10. DATA MANAGEMENT

Data management will be performed by Quintiles.

The data collected through third party sources will be obtained and reconciled against study data.

Adverse events and medical/surgical history will be classified according to the terminology of the latest version the Medical Dictionary for Regulatory Activities (MedDRA). Medications will be classified according to the AstraZeneca Drug Dictionary. All coding will be performed by Quintiles.

Data queries will be raised for inconsistent, impossible or missing data. All entries to the study database will be available in an audit trail.

The data will be validated as defined in the Data Management Plan. Quality control procedures will be applied to each stage of data handling to ensure that all data are reliable and have been processed correctly.

When all data have been coded, validated, signed and locked, clean file will be declared. Any treatment revealing data may thereafter be added and the final database will be locked.

11. EVALUATION AND CALCULATION OF VARIABLES BY ASTRAZENECA OR ITS REPRESENTATIVE

11.1 Calculation or derivation of efficacy variable(s)

11.1.1 Other significant adverse event (OAE)

During the evaluation of the AE data, an AstraZeneca medically qualified expert will review the list of AEs that were not reported as SAEs and DAEs (discontinuation of IP due to AE). Based on the expert's judgement, significant AEs of particular clinical importance may, after consultation with the Global Patient Safety Physician, be considered OAEs and reported as such in the CSR.

Examples of these are marked haematological and other laboratory abnormalities, and certain events that lead to intervention (other than those already classified as serious), dose reduction or significant additional treatment.

11.2 Calculation or derivation of pharmacokinetic variables

The PK analysis of the plasma concentration data for olaparib will be done at AstraZeneca R&D. The actual sampling times will be used in the final PK parameter calculations, except for the pre-dose sample for which the time will be set to zero. All PK computations will be performed using Phoenix™ for WinNonlin.

Patients who withdraw from the study following dosing, but prior to study completion, will be included in the PK analysis provided they have evaluable profiles over the planned collection period. Patients with partial data will be evaluated on a case-by-case basis to determine if sufficient data are available for meaningful analysis.

If sufficient data are available for estimation, the following single-dose PK parameters will be calculated for olaparib in Part A:

- Maximum plasma concentration (C_{max}) obtained directly from the observed concentration versus time data
- Time to maximum plasma concentration (t_{max}) obtained directly from the observed concentration versus time data
- Area under the plasma concentration-time curve from zero to the time of the last measurable concentration (AUC_{0-t}) calculated by linear up/log down trapezoidal summation
- Area under the plasma concentration time curve from zero (pre-dose) extrapolated to infinity (AUC) calculated by linear up/log down trapezoidal summation and extrapolated to infinity by addition of the last quantifiable concentration divided by the terminal rate constant: $AUC_{0-t} + C_{last}/\lambda_z$.

- Apparent plasma clearance (CL/F)
- Terminal half-life ($t_{1/2}$). Visual assessment will be used to identify the terminal linear phase of the concentration-time profile
- Apparent volume of distribution (V_z/F)
- Terminal rate constant (λ_z) estimated by log-linear least squares regression of the terminal part of the concentration-time curve
- Free C_{max} (C_{max} of unbound olaparib); calculated by multiplying total C_{max} value by estimated protein binding
- Free AUC (AUC of unbound olaparib); calculated by multiplying total AUC by estimated protein binding
- Unbound CL/F (CL/F of unbound olaparib); calculated from Dose/Free AUC.

Additional PK parameters may be determined if deemed appropriate.

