2.3 Exploratory objectives

Table 3 Exploratory objective

Exploratory objective	Exploratory outcome variables
To explore changes in protein binding of olaparib and the subsequent effects on its PK in patients with varying degrees of hepatic function.	In Part A, Plasma protein binding at 1 hour after dosing, used to calculate free C_{max} (C_{max} of unbound olaparib), free AUC (AUC of unbound olaparib) and unbound CL/F (CL/F of unbound olaparib).

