Day	Time (h)	Dose	PK blood sample ^a	Protein binding sample ^b
1	Pre-dose		X	
	0	X		
	0.25		X	
	0.5		X	
	1		X	X
	1.5		X	
	2		X	
	3		X	
	4		X	
	6		X	
	8		X	
	12		X	
	2	24		X
3	48		X	
4	72		X	
5	96		X	

PK pharmacokinetic

^a Venous blood samples (4 mL) for determination of olaparib in plasma.

^b Protein binding sample (3 mL) to determine the free fraction of olaparib in plasma

Table 6 Study plan – Part B (continued access to olaparib)

Visit Number	6 ^a	7	8	9	10	Subsequent on-treatment visits every 4 weeks ^b Visit 11 onwards	Study treatment discontinued	Follow-up 30 (±7) days after last dose of study medication
Day	1 ^a	8	15	22	29	Day 1 of next visit period (Equals Day 57 [Week 9] then Day 85 [Week 13], etc)		
Visit window		±3d	±3d	±3d	±3d	±7d	±7d	±7d
Physical examination ^c	X							
Vital signs (BP, pulse, temperature)	X	X	X	X	X	X	X	X
ECOG performance status	X							
Resting standard 12-lead ECG	X					X		X
Haematology ^d /clinical chemistry	X ^d	X	X	X	X ^d	X ^d	X ^d	X ^d
Urinalysis ^e	X	X	X	X	X	X	X	X
Adverse events	X	X	X	X	X	X	X	X
Previous and concomitant medications	X	X	X	X	X	X	X	X
Olaparib dispensed/returned ^f	X				X ^e	X ^e	X	

BP blood pressure; ECG electrocardiogram; ECOG Eastern Cooperative Oncology Group

Note: A pregnancy test will be conducted only in the event of a suspected pregnancy during the study.

^a Baseline safety assessments must be in accordance with the study inclusion and exclusion criteria

^b Visit to take place on Day 1 of a 4 week (28 day) visit period. Visits will continue for 12 months from the date the last patient enters Part B.

^c After baseline, it is not necessary to record any physical examination details on the CRF; any clinically significant changes should be recorded as AEs.

^d Haematology assessment to include prothrombin time for patients with mild or moderate hepatic impairment at every visit
Additional haematology assessments will be performed on Day 1, then monthly for 6 months, at discontinuation, and at the 30-day follow-up visit (see Section 6.4.5).

^e Protein, blood, glucose and bilirubin. Urinalysis to be conducted at every visit for patients with hepatic impairment. After baseline, urinalysis is only required for patients with normal hepatic function if clinically indicated.

^f Sufficient study treatment should be dispensed for at least each treatment period plus overage; however additional treatment can be dispensed to patients to last longer in accordance with local practice.

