3.2 Rationale for study design, doses and control groups

This study has been designed to investigate the effects of hepatic impairment on the PK of olaparib. Multiple dose PK of olaparib have previously been shown to be predictable and following twice daily dosing of the tablet formulation there is little accumulation on multiple dosing, therefore a single dose study is justified. Patients' hepatic function will be classified based on the Child-Pugh Classification system, in accordance with CHMP guidance [[CPMP/EWP/2339/02](#)].

Patients with hepatic metastases and/or hepatocellular carcinoma (HCC) are eligible for the study, providing the hepatic metastases or HCC are not the sole reason for any changes in liver function satisfying the criteria for mild or moderate hepatic impairment as defined by the Child Pugh criteria. Patients must have globally impaired hepatic function to participate in the study as the type of hepatic impairment that affects drug disposition is more related to liver cirrhosis and fibrosis i.e. to factors affecting the ability of the drug to enter the hepatocyte, rather than drug metabolism per se. Hepatocellular carcinoma and hepatic metastases do not have the same effect on general hepatocyte permeability that is seen in global hepatic impairment (e.g. related to cirrhosis or fibrosis). Since the liver has very large capacity for drug metabolism, a reduction in the amount of healthy functioning liver (due to the presence of carcinoma/metastases) does not necessarily have any impact on drug clearance. For this reason, studies performed in patients with 'hepatic impairment solely due to liver metastases' are not considered to be valid hepatic impairment studies by regulatory authorities. The aim of the study is to look at the exposure of olaparib in patients with 'globally impaired hepatic function', hence the categorisation of the degree of impairment for an individual patient will be based upon Child-Pugh criteria.

The impact of hepatic impairment on protein binding of olaparib will also be studied, since plasma protein binding is often altered in patients with impaired hepatic function.

Due to existing pre-clinical toxicology data it is not possible to use healthy volunteers for this study and therefore the study is being conducted in patients with advanced solid tumours.

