6.5.2 Determination of drug concentration

The plasma samples collected for protein binding determination will undergo equilibrium dialysis at Covance prior to the determination of concentrations of olaparib in the resulting plasma dialysate.

Samples for the determination of olaparib concentrations in plasma (total concentration) and plasma dialysate (free concentration) will be analysed by Covance on behalf of the Clinical Bioanalysis Alliance, AstraZeneca R&D using appropriate bioanalytical method(s). Full details of the bioanalytical method(s) used will be described in a separate bioanalytical report.

Results will only be reported for plasma samples shipped within a timeframe for which the stability of olaparib in the samples has been validated and shown to be acceptable.

Additional analyses may be conducted on the plasma samples to investigate reproducibility of incurred samples. Any results from these exploratory analyses will not be reported in the CSR but will be reported separately in a bioanalytical report.

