- If, at a given time point, 50% or less of the plasma concentrations are NQ, the mean, SD, geometric mean, %CV, and %GCV will be calculated by substituting the limit of quantification (LOQ) for values which are NQ.
- If more than 50%, but not all, of the concentrations are NQ, the mean, geometric mean, SD, %CV, and %GCV will be reported as not calculable (NC).
- If all the concentrations are NQ, the geometric mean and mean will be reported as NQ and the SD, %CV, and %GCV as NC.

The PK parameters will be rounded for reporting purposes both in the summary tables and by-patient listings. For the calculation of descriptive statistics and the statistical analysis, rounded values as presented in the data listings will be used. Except for raw measurements (such as C_{\max} and t_{\max}), all other derived PK parameters will be reported to 3 significant digits.

The PK data will be presented by hepatic function group (moderate hepatic impairment, mild hepatic impairment or normal hepatic function).

The goal of the statistical analysis in Part A is to estimate the effect of hepatic function on the PK of olaparib. Following log-transformation, C_{\max} and AUC (or AUC_{0-t} , if AUC is not adequately estimable) of olaparib will be separately analysed by analysis of variance (ANOVA), fitting a term for hepatic function group (moderate hepatic impairment, mild hepatic impairment or normal hepatic function).

The analysis will be carried out to compare the ratio of geometric means (gmeans) of the following groups:

1. Child-Pugh A classified patients (mild hepatic impairment) compared to patients with normal hepatic function (controls).
2. Child-Pugh B classified patients (moderate hepatic impairment) compared to patients with normal hepatic function (controls).

The results of these analyses will be presented in terms of geometric means for each hepatic function group. The ratio of geometric means of each hepatically impaired group compared to the normal group (mild/moderate: controls) will be presented with the respective 1-sided 95% upper confidence limit.

The possibility that hepatic impairment has a clinically relevant effect on the exposure of olaparib will be considered if the upper 1-sided 95% confidence limit for the ratio does not lie below the limit of 2, where the limit of 2 implies a doubling in exposure.

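### Section 11.2 derives free Cmax and free AUC by multiplying total exposure by protein binding rather than by the unbound fraction; taken literally, this gives bound exposure

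*Protocol*

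**What the plan says.** Protocol section 11.2 lists three unbound parameters for Part A. Free Cmax is "calculated by multiplying total C_{max} value by estimated protein binding". Free AUC is "calculated by multiplying total AUC by estimated protein binding". Unbound CL/F is "calculated from Dose/Free AUC".

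Other sections describe what the binding sample yields. Footnote b to Table 5 (section 3.1) reads "Protein binding sample (3 mL) to determine the free fraction of olaparib in plasma". Section 6.5.2 says that after equilibrium dialysis "olaparib concentrations in plasma (total concentration) and plasma dialysate (free concentration) will be analysed". The sample is taken once, 1 hour after dosing.

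The unbound parameters serve the exploratory objective in section 2.3: "To explore changes in protein binding of olaparib and the subsequent effects on its PK in patients with varying degrees of hepatic function". Section 3.2 gives the reason: "plasma protein binding is often altered in patients with impaired hepatic function".

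**The concern.** Unbound exposure is total exposure times the unbound fraction. Section 11.2 names protein binding as the multiplier, and in its ordinary sense, which is how section 3.2 uses it, that is the bound share. The resulting product is the exposure to bound drug under a label that says unbound.

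The slip matters because bound exposure also lies between zero and total exposure, so a wrong value need not look impossible. The derivation also crosses several hands: section 12.2.2 gives the assay to the bioanalytical laboratory, the parameter calculation to the sponsor's pharmacokineticist, and the summaries and statistics to the contract organisation. Each could take the written formula at face value. What is at stake is the answer to the exploratory question. If impairment lowers binding, free exposure at a given total exposure rises, while the quantity as written falls.

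**Working it through.** **Inputs.** The three formulas come from section 11.2, and the meaning of the assay results from Table 5 footnote b and section 6.5.2. The protocol states no binding value, so the unbound fractions below are assumptions, taken as one value per group for illustration. There is no figure in the plan to reproduce.

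**1. Level of free exposure.** Let T be total AUC and fu the unbound fraction.
- Correct: free AUC = fu × T.
- As written, with binding read as the bound fraction: (1 − fu) × T.
- As written over correct: (1 − fu)/fu.

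| Assumed fu | (1 − fu)/fu |
|---|---|
| 0.05 | 0.95/0.05 = 19 |
| 0.10 | 0.90/0.10 = 9 |
| 0.20 | 0.80/0.20 = 4 |
| 0.30 | 0.70/0.30 = 2.3 |
| 0.50 | 0.50/0.50 = 1 (no error in level) |

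The same factor applies to free Cmax. Unbound CL/F has free AUC in its denominator, so it is understated by that factor: at fu 0.20 it would be a quarter of its correct value.

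**2. Ratio of impaired to normal.** Let R be the ratio of total AUC, with fuN and fuI the unbound fractions in the normal and impaired groups.
- Correct ratio: R × fuI/fuN.
- As written: R × (1 − fuI)/(1 − fuN).

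When fuI exceeds fuN, the correct ratio is above 1 if R > fuN/fuI, and the written one is below 1 if R < (1 − fuN)/(1 − fuI). The direction reverses between those two bounds.

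| fuN → fuI (assumed) | Correct ratio at R = 1 | As written at R = 1 | R over which direction reverses |
|---|---|---|---|
| 0.05 → 0.08 | 1.60 | 0.968 | 0.625 to 1.033 |
| 0.10 → 0.15 | 1.50 | 0.944 | 0.667 to 1.059 |
| 0.10 → 0.20 | 2.00 | 0.889 | 0.500 to 1.125 |
| 0.20 → 0.30 | 1.50 | 0.875 | 0.667 to 1.143 |
| 0.30 → 0.40 | 1.33 | 0.857 | 0.750 to 1.167 |
| 0.50 → 0.60 | 1.20 | 0.800 | 0.833 to 1.250 |

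For example, with 0.20 → 0.30 the lower bound is 0.20/0.30 = 0.667 and the upper bound 0.80/0.70 = 1.143.

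**3. Above the window.** At R = 1.2 with 0.20 → 0.30, the correct ratio is 1.2 × 1.5 = 1.80 and the written one 1.2 × 0.875 = 1.05. With 0.10 → 0.15 they are 1.80 and 1.13. Both now point upward, but the written rule hides most of the increase.

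**4. Reach.** Section 12.2.2 fits its model to log Cmax and log AUC (or AUC to the last measurable point), which "of olaparib will be separately analysed by analysis of variance (ANOVA), fitting a term for hepatic function group". The limit of 2 applies to those ratios, and section 12.3 sizes the study on log AUC. Section 11.2 computes total Cmax and AUC without any binding value, so none of these is touched.

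**The case against.** The best defence is that this is loose wording. Section 11.2 labels its outputs as unbound, Table 5 says the sample gives the free fraction, and section 6.5.2 assays the free concentration directly. Sections 2.3 and 3.1 use protein binding as the name of the measurement, so the phrase in 11.2 may be shorthand for the assay result. A pharmacokineticist would probably apply the free fraction, and a free Cmax several times too high could be noticed against the 1-hour dialysate result. Much of this stands: a slip of wording is at least as likely as a wrong intention. It does not rescue the text, because no section defines the multiplier as the unbound fraction and the formula is given twice.

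Four stronger readings are tempting, and the protocol does not support them.
- A reader might infer that every unbound result is wrong. That requires the bound fraction actually to be used, and the protocol cannot show what is programmed.
- A reader might infer that the hepatic effect will reverse. Reversal needs a total-AUC ratio near 1 together with a change in fu, and neither is known.
- A reader might infer that the study could wrongly declare hepatic impairment harmless. The stated criterion for a clinically relevant effect rests on total exposure, and no decision rule uses free exposure.
- A reader might fault the absence of a formal model for free exposure. Descriptive reporting of an exploratory variable is legitimate, such detail is commonly left to the SAP, and a model fitted to wrongly derived values would carry the error rather than reveal it.

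**Conclusion.** Wrong as written, of moderate severity. The stated rule for free Cmax and free AUC, followed literally, yields bound exposure; unbound CL/F follows it; and the rule contradicts the protocol's own sampling and assay text.

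If executed as written, the error in level is (1 − fu)/fu, and the group ratio is pulled down where impairment raises fu. Reversal is confined to total-AUC ratios around 1. The research hypothesis in section 1.2 expects no clinically significant PK change, so that region is a relevant one, but the figures rest on assumed unbound fractions and on literal execution. The consequence is limited to the exploratory objective.

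**What to change.** In section 11.2, for both free Cmax and free AUC, replace protein binding as the multiplier with the estimated unbound fraction, defined as fu = free (dialysate) concentration divided by total plasma concentration, both from the 1-hour protein binding sample. Keep unbound CL/F as dose divided by free AUC; it is correct once free AUC is. Confirm that the programmed derivation uses fu.

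The cost is one phrase in the protocol, carried into the SAP if it repeats the formula, and one check of the derivation. No new samples, assays or analyses are needed.

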11.3 Calculation or derivation of efficacy variable(s) (Not applicable)

11.4 Calculation or derivation of patient reported outcome variables (Not applicable)

11.5 Calculation or derivation of pharmacodynamic variables(s) (Not applicable)

11.6 Calculation or derivation of pharmacogenetic variables (Not applicable)

11.7 Calculation or derivation of health economic variables (Not applicable)

12. STATISTICAL METHODS AND SAMPLE SIZE DETERMINATION BY ASTRAZENECA OR DELEGATE

12.1 Description of analysis sets

The study physician, pharmacokineticist, and statistician will agree on the strategy for dealing with data affected by protocol deviations before any formal statistical analysis is performed.

The analysis sets are defined in [Table 11](#).

Table 11 **Definition of analysis sets**

Analysis Set	Population
PK analysis set	All patients who receive an olaparib dose and have full PK sampling up to 96 hours post-dose.
Evaluable for Safety	All patients who receive at least 1 dose of olaparib and for whom any post-dose data are available will be included in the safety population

If a patient has a major protocol deviation that affects the evaluability of the PK profile, then the patient will not form part of the PK analysis set.

Major protocol deviations include changes to the procedures that may impact the quality of the data, or any circumstances that can alter the evaluation of the PK. Examples include, but may not be limited to, vomiting following oral dosing occurring within the time frame of 2 times the median t_{max} , sample processing errors that lead to inaccurate bioanalytical results, incomplete dose administered, incomplete PK profile collected, and/or use of disallowed concomitant medication. In the case of a major protocol deviation, affected PK data collected will be excluded from the summaries and statistical analyses, but will still be reported in the study result listings. Major deviations will be listed and summarised in the CSR.

12.2 Methods of statistical analyses

The following text applies to demographic and safety analyses only; PK is discussed separately.

Statistical analyses will be performed by Quintiles under the direction of the Biostatistics Group, AstraZeneca using SAS[®] version 8.1 or higher and, where appropriate, additional validated software.

A comprehensive Statistical Analysis Plan (SAP) will be prepared before database lock. For qualitative variables, the population size (N for sample size and n for available data) and the percentage (of available data) for each class of the variable will be presented. Quantitative variables will be summarised using descriptive statistics, including n, mean, SD, median, minimum, and maximum values. Where appropriate, assessments will be summarised by visit.

The number of patients screened and included in the Evaluable for Safety analysis set will be summarised. Demographic and baseline characteristics will be summarised and listed for the Evaluable for Safety analysis set.

Treatment duration will be summarised. Treatment duration is based on the dates of first and last dose.

Study day will be calculated as follows:

Days prior to first dose: Study day = date – first dose date.

Days on or after first dose: Study day = date – first dose date + 1.

No imputations will be made for any missing data.

12.2.1 Database locks and data analyses

Part A

The database will be locked once all patients in the mild hepatic impairment and normal hepatic function groups have completed Part A. An interim analysis will be performed to compare the PK, safety and tolerability of olaparib in subjects enrolled in these 2 groups. The interim analysis will be reported in a full CSR.

Subsequently, after the last patient has completed Part A (including patients in the moderate hepatic impairment group), the database for Part A of the study will be locked and the data will be reported in a further CSR.

Part B

On completion of Part B, a further database lock will occur and the Part B data will be reported in a CSR addendum.

